12.5 Secondary and Exploratory Objectives

Refer to **Section 5** for the secondary objectives and endpoints. Secondary objectives are to compare effects on physical functioning / functional capacity, primary physiological determinants of VO_2peak , metabolic outcomes of interest, and subject-reported outcomes (PROs) of interest. The safety, feasibility, and acceptability of exercise training will also be evaluated.

Refer to **Section 5** for the exploratory objectives and endpoints. Exploratory objectives are to compare PSA response rates and describe metabolomics changes.

Secondary and exploratory endpoints are generally assessed at baseline, week 17, and at the end of week 36.

Descriptive comparisons of changes in secondary and exploratory endpoints will be done both:

- between baseline and the start of week 17 to assess the effect of exercise on changes due to ENZ + ADT, and
- between the start of week 17 and the end of week 36 to assess whether there is a lasting effect of the supervised exercise regimen after it is discontinued.

Continuous measures will generally be analyzed using a repeated measures model with the measure as the dependent variate and treatment arm and week of assessment as independent variates. Appropriate transformations will be used in cases where the measures the assumption of normally distributed errors would be violated.

Categorical measures will be analyzed using categorical data modeling techniques.

Whenever possible, transformation or categorization of secondary and exploratory measures will be done as reported in previously published studies in the field.

Eligibility rate is defined as the number of subjects found to be eligible for the study divided by the number approached for the study (i.e. screen fail rate). (Note: ineligible patients will not be randomized.) *Acceptance rate* is defined as the number of patients agreeing to participate divided by total number randomized.

Adherence rate is defined as the proportion of patients adhering to the exercise intervention (obtained from weekly exercise training attendance logs). *Attrition rate* is defined as the proportion of subjects who complete the 16 week exercise training program.

For analysis of metabolomics, PCA analysis will be used to reduce the large number of correlated factors into a smaller number of dimensions. Unless otherwise noted, all analyses will be done separately for the usual care and exercise groups. Of primary interest is the association of metabolomic biomarkers with changes in both VO₂peak and HOMA-IR. Changes in metabolite concentrations and VO₂peak or HOMA-IR will be compared between the usual care and exercise groups using ANOVA. Correlation analysis and linear regression will be used to describe the relationship between metabolomics biomarker changes and VO₂peak or and HOMA-IR. Nominal statistical significance will be defined as p<0.05.

In addition, the maximum PSA change from baseline in each patient will be described using waterfall plots. The PSA response rate, defined as the proportion of men with a ≥80% decline in PSA from baseline, will be reported for each arm. The median decrease in PSA will also be reported for each arm.

Sensitivity analyses will be performed repeating primary endpoint and key secondary endpoint analyses using Last Value Carried Forward (LOCF) methods. The intent of this sensitivity analysis is to assay the robustness of results observed in the modified ITT population.

Adjustment for multiple comparisons is not planned for secondary or exploratory measures.

Rates of adverse events, classified by CTCAE v4.0, will be displayed by body system and preferred term for each arm.

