5 OBJECTIVES AND ENDPOINTS

All endpoints will be evaluated at the time points specified in the Schedule of Events at the beginning of **Section 9**. See **Section 12** for Statistical Methods and Data Analysis. Key comparisons will be the change from Day 1 (week 1) to Day 113 (week 17), which corresponds to the end of the 16 week exercise training program for Arm B, and from Day 1 (week 1) to Day 252 (week 37), which corresponds to the end of the 32 weeks of treatment with enzalutamide and ADT for both Arms.

	Objective	Endpoint	Analysis
Primary	Compare cardiopulmonary function in usual care vs. exercise training arms	Change in $\text{VO}_{2\text{peak}}$ with usual care or exercise training at 16 weeks from baseline	See Section 12.1 to 12.4
Key Secondary	Compare the effects on physical functioning / functional capacity	Objective assessments (i.e., chair-stand test, timed up and go, 6 minute walk distance) of functional capacity	See Section 12.5
Other Secondary	Compare the effects on primary physiological determinants of $\text{VO}_{2\text{peak}}$	Upper and lower extremity maximal muscular strength (voluntary one-repetition maximum [1-RM]) and muscular endurance (repetitions to fatigue at 70% of 1-RM and muscle cross sectional area of the dominant thigh (3.0 T magnetic resonance imaging)	See Section 12.5
Other Secondary	Compare the effects on metabolic outcomes of interest	Metabolic control (fasting glucose, insulin, glycosylated hemoglobin, HOMA-IR) and body composition (lean and fat body mass)	See Section 12.5
Other Secondary	Compare the effects on patient reported outcomes (PROs) of interest	Quality of Life (FACT-P), Fatigue (FACIT-F), and Leisure Time Exercise Habits (Godin Leisure Time Exercise Questionnaire)	See Section 12.5
Other Secondary	Evaluate safety, feasibility, and acceptability of exercise training	Eligibility rate, acceptance rate, adherence rate, attrition rate, and adverse event rate (CTCAE v4.0) in each arm	See Section 12.5
Exploratory	Compare PSA response rates	Maximum decrease in PSA from baseline (waterfall plot)	See Section 12.5
Exploratory	Describe metabolomics changes	Targeted and untargeted metabolic profiling	See Section 12.5
Sensitivity	Assay the robustness of results observed in analyses based on the modified ITT population	Primary and Key secondary endpoints, using Last Observation Carried Forward methods	See Section 12.5

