9.6 Treatment Period 1: ENZ-ADT plus either Usual Care or Exercise Training

Arm A, ENZ – ADT plus Usual Care: Beginning on Day 29 (week 5), subjects will be treated with androgen deprivation therapy (ADT) per standard of care (orchiectomy, GnRH agonist, or GnRH antagonist to maintain total testosterone <50 ng/dl for the remaining 32 weeks of the study). In addition, subjects will take enzalutamide (ENZ) 160 mg by mouth daily for the remaining 32 weeks of the study. The dosing of both the GnRH agonist and enzalutamide (160 mg daily) is the standard-of-care dosing. The treatment duration of approximately 8 months was selected to achieve maximal efficacy while minimizing toxicity and is based on intermittent hormonal therapy regimens studied in Phase III clinical trials.^{22,23} Concomitant medication will be evaluated at every clinic visit during enzalutamide therapy. Concomitant medications include all vitamins, herbal remedies, over the counter, and prescription medications.

Arm B, ENZ – ADT plus Exercise Training: Beginning on Day 29 (week 5), Subjects randomly allocated to this group will receive the same ADT-ENZ regimen as described above. In addition, subjects will continue the defined exercise training initiated during the Lead-In Period for a total of 16 weeks (through Day 113, week 17).

The window is ± 7 days for this period, EXCEPT Day 29 (week 5) which has a window of ± 3 days. See **Schedule of Events**, above.

Subject data to be collected during Treatment Period 1 includes:

- Physical Exam
- Height, Weight, BMI
- Vital Signs
- Performance Status (ECOG)
- Concomitant Medications
- Adverse Events
- CBC with Platelets (hemoglobin, hematocrit, platelet count, white blood cell count, total [absolute] neutrophils)
- Serum Chemistry (sodium, potassium, chloride, total CO₂ [bicarbonate], calcium, BUN, creatinine, glucose, albumin, total bilirubin, total protein, alkaline phosphatase, AST, ALT)
- Testosterone (Day 57 and 113)
- PSA
- CPET (Day 29 and Day 113)
- Chair Stand (Day 113)
- Timed Up and Go (Day 113)
- 6 Minute Walk Distance (Day 113; **Duke patients only**)
- Muscular Strength (*at least 24 hours before or after CPET on Week 4, Week 10 (not in conjunction with CPET) and week 17 in treatment period 2*)
- Muscle CSA (MRI; Day 113; **protocol v1-v15 only**)
- Muscular Endurance (*must be at least 24 hours before or after CPET to allow for adequate recovery on week 4, week 10 (not in conjunction with CPET) and week 17 in treatment period 2*)

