9.7 Treatment Period 2: ENZ-ADT

Subjects on both arms will continue ADT per standard of care and enzalutamide through Week 37 (Day 252).

The window is -7/+30 days for this period. See **Schedule of Events**, above.

Subject data to be collected during Treatment Period 2 includes:

- Physical Exam
- Height, Weight, BMI
- Vital Signs
- Performance Status (ECOG)
- Concomitant Medications
- Adverse Events
- CBC with Platelets (hemoglobin, hematocrit, platelet count, white blood cell count, total [absolute] neutrophils)
- Serum Chemistry (sodium, potassium, chloride, total CO₂ [bicarbonate], calcium, BUN, creatinine, glucose, albumin, total bilirubin, total protein, alkaline phosphatase, AST, ALT)
- Testosterone (Day 169 and 252)

- PSA
- FACT-P (Day 252)
- FACIT-Fatigue (Day 252)
- Godin Leisure Time Exercise Questionnaire (Day 252)
- Collect Pill Diary for Enzalutamide

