9.12.3 Correlative Assessments

All Correlative Assessments will be performed at Day 1 and Day 113 (see Schedule of Events at the beginning of this Section for details). Patient reported outcomes will also be performed at Day 252. In addition, a CPET will be performed at Day 29 to assess VO₂peak changes during the Lead-In Period and Metabolomics samples will be drawn at Day 57 to assess for early changes that may predict later changes in metabolic parameters. All samples will be collected in the fasting, pre-exercise state unless otherwise noted below.

Cardiopulmonary Exercise Testing (CPET)

Exercise Capacity will be assessed using a symptom-limited CPET on a motorized treadmill with expired gas analysis to determine VO₂peak, according to guidelines for clinical populations.⁹⁰ All CPET data will be recorded as the highest 30s value elicited during the CPET. During exercise, heart rate and rhythm will be monitored continuously using a 12-lead ECG. Equipment with similar technical specifications will be used across the two study sites to ensure reasonably accurate and precise results.

Physical Functioning / Functional Capacity

Physical Functioning / Functional Capacity will be assessed using the following assessments: chair-stand test, timed up and go, and 6 min walk distance outcomes as described previously.^{91 57,92,93} These measures will complement the exercise capacity measure.

Chair-Stand Test: The 5-repetition chair-stand test measured the time taken to complete 5 repetitions of the sit-to-stand maneuver. All sit-to-stand maneuvers will be performed from a chair without an arm rest at 43cm in height and 47.5cm in depth. Standardized instructions will be provided as follows: "By the count of 3, please stand up and sit down as quickly as possible for

5 times. Place your hands on your lap and do not use them throughout the procedure. Lean your back against the chair's backrest at the end of every repetition." Timing will start when the subject's back left the backrest and will be stopped once the back touched the backrest.

Timed Get Up and Go: Subjects will be required to stand up from a chair with armrests, walk 3m, turn around, return to the chair, and sit down. The time taken to complete this task will be measured in seconds with a stopwatch.⁹³

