12.4.2 Statistical Hypothesis, Model, and Method of Analysis

The primary analysis will be comparison of the change in peak oxygen uptake ($\Delta\text{VO}_2\text{peak}$) from week 1 to week 17 between the usual care and exercise training groups, using a t-test. The primary analysis will be done for complete cases, (i.e. patients with VO_2peak measured at baseline and at week 17) in the ITT population.

Descriptive comparisons of $\Delta\text{VO}_2\text{peak}$ will be done:

- between baseline and end of week 4 to assess the effect of exercise (or usual care) alone,
- between end of week 4 and start of week 17 to assess the effect of exercise during ENZ + ADT treatment, and
- between the start of week 17 and the end of week 36 to assess whether there is a lasting effect of the supervised exercise regimen after it is discontinued.

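### Section 12.5 uses the week 17 to week 36 change to judge a lasting effect of exercise; taken alone it measures change in the benefit after training stops, and Section 12 omits the Day 1 to Day 252 comparison named in Section 5

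*Combined protocol and SAP*

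**What the plan says.** Section 12.5 sets out two windows for the secondary and exploratory endpoints: "Descriptive comparisons of changes in secondary and exploratory endpoints will be done both". The first runs from baseline to the start of week 17 and addresses the effect of exercise on changes due to the drug treatment. The second runs from the start of week 17 to the end of week 36, and its stated purpose is "to assess whether there is a lasting effect of the supervised exercise regimen after it is discontinued". Section 12.4.2 gives VO2peak the same window and purpose: "between the start of week 17 and the end of week 36 to assess whether there is a lasting effect of the supervised exercise regimen".

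Section 5 names two key comparisons. One is Day 1 to Day 113. The other is "from Day 1 (week 1) to Day 252 (week 37), which corresponds to the end of the 32 weeks of treatment" with enzalutamide and ADT. Section 12 does not list this second comparison.

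Section 9.6 ends exercise training at Day 113. Section 9.7 keeps both arms on enzalutamide and ADT to Day 252. On what is measured late, Section 9.12.3 says "Patient reported outcomes will also be performed at Day 252". Section 9.7 and the Schedule of Events agree, listing FACT-P, FACIT-Fatigue and Godin at that visit.

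**The concern.** A lasting effect of training is most naturally the difference between arms that remains some time after training has ended, measured against the pre-randomisation starting point. The contrast in 12.5 starts when training ends, so the gain sits inside its starting value and is subtracted out. What is left is the later movement of that gain. A benefit held intact and a benefit that never existed give the same value on this contrast alone, and a benefit partly kept gives a value on the side of usual care.

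At stake is how the fatigue, quality-of-life and leisure-activity results after training are described. A report that follows the label in 12.5 and quotes only the second window could give a misleading account of durability. The comparison that would answer the question directly is named in Section 5 but has no place in the analysis section.

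**Working it through.** **Plan's own figure.** The plan gives no effect size, precision or decision rule for the week 17 to 36 comparison, so there is no stated figure to reproduce. The power statement in Section 12.6 concerns the primary endpoint and plays no part here.

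**Timing.** Start of week 17: 16 × 7 + 1 = Day 113, the end of training. End of week 36: 36 × 7 = Day 252, which Section 5 and the Schedule of Events label week 37. The two sections therefore refer to the same late visit.

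**Algebra.** Let D17 and D36 be the expected between-arm differences (exercise minus usual care, positive favouring exercise) at Day 113 and Day 252. Randomisation makes the expected baseline difference zero. Then:

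- baseline to week 17 contrast = D17
- week 17 to 36 contrast = D36 − D17
- baseline to Day 252 contrast = D36

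Write D36 = f × D17, where f is the share of the benefit kept and D17 is above zero. The week 17 to 36 contrast is (f − 1) × D17 and the baseline to Day 252 contrast is f × D17.

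The documents give no assumed difference for FACT-P, FACIT-F or Godin. The only between-arm difference they assume is 3.0 mL/kg/min for VO2peak (Section 12.6). It is used below only to put numbers into the formulas, because VO2peak is not measured at Day 252.

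| Share kept, f | Week 17–36 contrast | With D17 = 3.0 | Baseline–Day 252 contrast | With D17 = 3.0 |
|---|---|---|---|---|
| 1.2 | +0.2 × D17 | +0.6 | 1.2 × D17 | +3.6 |
| 1 | 0 | 0.0 | 1 × D17 | +3.0 |
| 0.75 | −0.25 × D17 | −0.75 | 0.75 × D17 | +2.25 |
| 0.5 | −0.5 × D17 | −1.5 | 0.5 × D17 | +1.5 |
| 0 | −1 × D17 | −3.0 | 0 | 0.0 |

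**Can the Day 252 difference be recovered from the two planned windows?** D17 + (D36 − D17) = D36, so the estimates add up exactly when the same patients contribute to both. That is not assured. The primary analysis population in Section 12.1 requires a baseline and a week 17 evaluation but no Day 252 evaluation, so a patient who misses Day 252 can enter the first window and not the second. An interval is also not available from the two results reported separately: the variance of the sum is Var(first) + Var(second) + 2 × Cov(first, second). The covariance is not reported, and it is not zero, because both windows use the same week 17 value.

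**Does the model supply the estimate?** Section 12.5 describes a repeated measures model with arm and week as explanatory terms. No arm-by-week term and no arm contrast at the last visit are stated. Fitted with those two terms only, the model has one arm difference common to all weeks and cannot separate D17 from D36.

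**Which outcomes are affected.** CPET after baseline is at Day 29 and Day 113 only. The chair stand, timed up and go and six-minute walk are at baseline and Day 113 only. Neither contrast can be computed for these from scheduled data. FACT-P, FACIT-F and Godin have all three time points.

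**The case against.** The strongest reply is that nothing is lost. Section 12.5 reports both windows, so a reader sees a positive difference followed by about zero when the benefit is kept, and zero followed by zero when there was none. Section 5 already names the Day 1 to Day 252 comparison, and 12.5 refers back to Section 5 for its objectives and endpoints. The comparisons are descriptive, and no rule says that a zero or negative result means no lasting effect. The week 17 to 36 change also answers a fair question: both arms stay on drug treatment, and if usual care went on declining while the exercise arm held steady, the contrast would be positive.

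Most of this stands, and it limits the point. A reader might infer that the plan cannot show durability, or that a real lasting benefit would be reported as absent or reversed. The documents do not support either inference, because both windows are to be presented and no decision rule is attached. For the same reason, a power or significance calculation for this contrast would rest on a test that the plan does not specify. A reader might also take Section 5 as defining the lasting effect. It does not: it ties Day 252 to the end of drug treatment.

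Three things remain. The purpose stated in 12.5 is attached to the contrast that does not measure it when taken alone. The direct estimate has no specified analysis or interval. And adding the two windows gives the right answer only when the same patients contribute to both.

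**Conclusion.** The point holds as a mismatch between a stated purpose and the contrast assigned to it, together with a key comparison in Section 5 that Section 12 drops. With a week 17 benefit of D17 and a share f kept, the contrast returns (f − 1) × D17 where the retained benefit is f × D17. The gap between the two is always D17, whatever share is kept. This needs only a zero expected baseline difference, which randomisation supplies. The statements about sign also need D17 to favour exercise.

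The practical reach is small: three descriptive patient-reported outcomes in a 40-patient trial. The primary test is unaffected. The 3.0 figure should not be read as the size of an error in any planned result, because it belongs to VO2peak, and the documents give no expected difference for the outcomes that are affected. The correction is still worth making, because it costs almost nothing and gives the durability question its own estimate and interval.

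**What to change.** In Section 12.5:

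1. Add the Day 1 to Day 252 comparison from Section 5. State that the lasting-effect estimate for FACT-P, FACIT-F and Godin is the between-arm difference in change from baseline to Day 252, with a 95% confidence interval. An equivalent route is the arm contrast at the Day 252 visit from the repeated measures model with an arm-by-week term added.
2. Keep the week 17 to 36 comparison, relabel it as change after supervised training stops, and say that it is to be read beside the baseline-to-week-17 difference.
3. State which patients enter each comparison, so that the three differences can be related to one another.

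In Section 12.4.2, align the label of the matching VO2peak bullet, and note that the schedule has no CPET at Day 252 to feed it.

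The cost is a wording change in the analysis section. No visit, assessment or patient is added, and the primary analysis stays as it is.

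### Section 12.5 lists only arm and week for the secondary repeated-measures model; fitted as listed, it has no parameter for the between-arm difference in change that the plan asks for

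*Combined protocol and SAP*

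**What the plan says.** **Target.** Section 5 states: "Key comparisons will be the change from Day 1 (week 1) to Day 113 (week 17"); it adds the change from Day 1 to Day 252. Section 12.5 lists descriptive comparisons of change over two intervals. One runs from baseline to week 17. The other runs "between the start of week 17 and the end of week 36 to assess whether there is a lasting effect" of supervised exercise.

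**Model.** The next sentence of Section 12.5 says continuous measures will generally be analysed with "a repeated measures model with the measure as the dependent variate and treatment arm and week of assessment as independent variates". Neither that section nor any other names an arm-by-week term, a baseline covariate, a covariance structure or the coefficient to report.

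**Visits.** Section 12.5 says "Secondary and exploratory endpoints are generally assessed at baseline, week 17, and at the end of week 36". Section 9.12.3 is narrower: "All Correlative Assessments will be performed at Day 1 and Day 113", and "Patient reported outcomes will also be performed at Day 252". Section 9.6 agrees for the functional tests, for example "Chair Stand (Day 113"), and Section 9.7 does not repeat them. Section 9.6 lists strength and endurance at "Week 4, Week 10 (not in conjunction with CPET) and week 17 in treatment period 2", in addition to baseline.

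**Separate methods.** The primary endpoint has a t-test on change (12.4.2). The metabolomics analysis compares changes in metabolites and in VO2peak or HOMA-IR between arms by ANOVA (12.5).

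**The concern.** The plan's question is whether change differs between arms. In a model for the raw measure over time, the arm-by-week term answers it. In a model for the follow-up value, the arm term answers it once baseline is a covariate. The model sentence names neither.

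If someone fits the two listed terms and reports the arm coefficient, the key secondary functional endpoints get a diluted effect mixed with any chance baseline difference. The lasting-effect question for the patient-reported outcomes (PROs) would have no model estimate. The LOCF sensitivity analysis in 12.5 repeats the key secondary analyses, so it would inherit the gap.

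The trial is open label (6.1.4), and its sample size was revised after a look at between-arm data (12.6). That is further reason to settle the reported term before analysis.

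**Working it through.** **The plan's own figures.** No figure is given for the secondary model. The only current power figure is for the primary t-test (12.6): 20 per arm, effect size 0.68, one-sided 0.10, 80% power. It reproduces at 80.1% with the exact noncentral t and does not depend on this point.

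**Step 1: the contrast under the listed terms.** Write the mean as a + b·arm + g(week). Change from week s to week t is g(t) − g(s) in both arms, so the between-arm difference in change is 0. A design-matrix check gives a zero contrast vector for baseline to week 17 in both the two-visit and the three-visit layout. This needs no assumption about variances or correlations.

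**Step 2: baseline must be an outcome for two-visit endpoints.** These are chair stand, timed up and go, 6-minute walk distance (6MWD) and body composition. Muscle cross-sectional area and the fasting metabolic measures join them where collected under protocol v1–v15. With only baseline and week 17 available, leaving baseline out leaves one value and nothing repeated.

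**Step 3: what the arm term estimates.** It is a weighted average of the arm differences at each visit. Set the true baseline difference to 0 and the week-17 difference to 1.

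- Two visits, equal variances: (0 + 1)/2 = 0.50.
- Two visits, unstructured covariance: the weight on week 17 is (v0 − c)/(v0 + v17 − 2c), where v0 and v17 are the variances and c the covariance. Assume correlation 0.7 and baseline SD 1. With a week-17 SD of 1.2 it is (1 − 0.84)/(1 + 1.44 − 1.68) = 0.16/0.76 = 0.21. With 0.8 it is (1 − 0.56)/(1 + 0.64 − 1.12) = 0.44/0.52 = 0.85.
- PROs, three visits, equal variances and a common correlation: (0 + 1 + x)/3, where x is the share of the effect remaining at Day 252. For x = 0, 0.5 and 1 this gives 0.33, 0.50 and 0.67. The true week-17-to-Day-252 contrast would be −1.0, −0.5 and 0; the listed model gives 0 in all three cases.

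**Step 4: simulation.** With two visits, 20 per arm, equal variances and a true week-17 difference of 1 SD, 40,000 simulated trials gave these means:

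| Correlation (assumed) | Literal arm term | Change score | ANCOVA |
|---|---|---|---|
| 0.5 | 0.501 | 0.999 | 1.000 |
| 0.7 | 0.499 | 0.998 | 0.999 |
| 0.9 | 0.500 | 1.001 | 1.001 |

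A separate run of 400 trials per setting compared the literal arm term with the arm-by-week term. At correlations 0.5, 0.7 and 0.8 the true differences in change were 0.680, 0.527 and 0.430 SD. The arm term averaged 0.346, 0.249 and 0.220; the arm-by-week term averaged 0.683, 0.548 and 0.433.

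**Step 5: chance baseline imbalance.** With 20 per arm, one standard error of the baseline difference is √(2/20) = 0.316 SD. At correlations 0.5, 0.7 and 0.9:

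- Literal arm term: 0.5(1 + ρ) × 0.316 = 0.237, 0.269 and 0.300 SD.
- Change score: −(1 − ρ) × 0.316 = −0.158, −0.095 and −0.032 SD.
- ANCOVA: about 0.

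The documents give no SDs or correlations for these endpoints in this trial, so the ranges are assumptions. The 20-per-arm figures in Steps 4 and 5 do not apply to 6MWD, which is measured in Duke patients only. Nor do they apply to the measures discontinued at v16.

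**The case against.** The model sentence can be read as a list of variables rather than a complete formula, and it says measures will *generally* be analysed this way. A statistician who sees the change comparisons directly above it may well add the interaction. Those comparisons already state the wanted contrast, and for a two-visit endpoint the arm comparison of change equals the arm-by-week contrast. The endpoints are secondary or exploratory, in what the protocol itself calls a pilot study, with no multiplicity adjustment planned.

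Most of this stands. It limits the point to under-specification whose harm is conditional on two steps the documents do not state: an additive fit, and reporting its arm term.

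It does not remove the point. The change comparisons have no method attached, and the only general method given for continuous measures lists terms that cannot estimate them. A report could then hold two different answers with no rule for choosing between them.

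A reader might also infer that the key secondary effects will be halved. The documents do not support that: one half requires equal variances, and no covariance structure is given.

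**Conclusion.** The point holds as a gap in specification. Followed literally, with baseline among the outcomes, the stated model sets the between-arm difference in change to zero for every pair of visits. That part is algebra. Its arm term is then a weighted average of the visit differences including baseline. For two-visit endpoints this is 0.50 of the week-17 effect under equal variances, and 0.21 or 0.85 in the two unequal-variance examples. For PROs it is 0.33 to 0.67, under equal variances and a common correlation.

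Three stronger inferences are not supported:

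- That the plan commits to an additive model: the text leaves room for an interaction.
- That the primary result is affected: it rests on a t-test of change.
- That planned power is lost: no power is stated for these endpoints.

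It should be fixed before analysis, because the remedy is small and uses data already collected.

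**What to change.** In Section 12.5:

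1. For endpoints with more than two visits (PROs, strength, endurance), add the arm-by-week term. Report the between-arm difference in change from baseline to week 17. For PROs, also report baseline to Day 252 and week 17 to the end of week 36.
2. For the two-visit endpoints listed in Step 2 of the working, compare week-17 values between arms by ANCOVA adjusted for baseline, and report the arm coefficient. Under randomisation this has the same target as the difference in change.

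**Cost.** One or two sentences; no new visits, data or patients. ANCOVA uses one degree of freedom (37 residual instead of 38 with 20 complete per arm; fewer for 6MWD). The interaction uses two for PROs and three for strength and endurance.

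ANCOVA is partly a precision choice: in the simulation its variance was 0.77, 0.87 and 0.98 of the change score's at correlations 0.5, 0.7 and 0.9. Its price is that it drops patients missing either value of that endpoint. The modified ITT definition in 12.1 requires a baseline and a week-17 evaluation without saying of which endpoint, so it does not guarantee both. A likelihood-based two-visit model with the arm-by-week term would keep such patients.
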